Does a ketamine Infusion decrease post-operative narcotic consumption after gastric bypass surgery?

NCT03001843

Most recent approval: 2/22/2017
UNIVERSITY OF FLORIDA ACADEMIC HEALTH CENTER

Does a ketamine Infusion decrease post-operative narcotic consumption after gastric bypass surgery?

Investigators: [name] CRNA PI, [name] MD , and [name] MD

Abstract: Among the negative side effects of narcotics is respiratory depression. The risks of respiratory depression are exacerbated when coupled with pre-existing sleep apnea. The obese patient population is predisposed to sleep apnea and are a growing population, increasingly presenting for gastric bypass surgery as a means to lose the excess weight. One drug which can decrease the need for narcotics while still delivering good pain relief is ketamine. It is our hypothesis that an intra operative infusion of ketamine will decrease the amount of post-operative narcotics required for adequate pain relief and thereby the patients will be exposed to fewer narcotic side effects.

Background: According to the Centers for Disease Control (CDC), approximately one third of American adults, about 78.6 million, are obese. Obesity contributes greatly to healthcare costs in this country accounting for \$147 billion in 2008, according to the most recent data available from the CDC.¹ The health risks associated with obesity cited by the CDC include, but are not limited to coronary heart disease, high blood pressure, type 2 diabetes, cancers, stroke, liver and gall bladder disease, sleep apnea, and osteoarthritis¹.

Several treatments for obesity exist with varied efficacy and long term success rates. With caloric reduction as the initial treatment it was found that after 6 months there is a reduction in initial body weight of about 8%; however beyond 4-5 years the amount of weight loss drops off to 4%.² In contrast Gastric Bypass Surgery has shown “that patients lose about 2/3 to 3/4 of their excess weight over the first two years. Longer term studies have shown that on average patients keep off at least 1/2 of the excess over 5 to 15 years.”³

Obesity is an epidemic in America and surgical interventions have been shown to provide greater and longer lasting weight loss compared to conservative measures such as caloric restriction. Among surgical interventions, gastric bypass has shown better maintenance of weight loss than vertical banded gastroplasty.⁴ It is therefore probable that anesthesia providers will be seeing an increasing number of obese patients presenting for gastric bypass in the coming years. The tremendous healthcare costs related to obesity as well as the high success rate of gastric bypass “a loss of 50% of excess weight as long as 14 years postoperatively”⁴ make this an important issue for anesthesia providers. Managing this group of patients with their co-morbidities presents its own unique challenges and one of those challenges is effective post-operative pain control while maintaining adequate ventilation as this group is highly prone to sleep apnea even before undergoing an anesthetic and administration of narcotics.

The dangers of sleep apnea in this group should not be taken lightly. In a closed claims analysis from 1990 through 2009 it was found that there were 92 cases probably or definitely related to post-operative narcotic related respiratory depression and in 77% of those cases, the patient suffered death or severe brain damage. The review article found that the typical patient who would suffer an adverse

event due to narcotic related respiratory depression was “an obese adult patient with severe OSA receiving opioids postoperatively without continuous electronic monitoring, oxygen supplementation or CPAP” and obese adult patients are the population receiving laparoscopic gastric bypass. In the American Society of Anesthesiologists Practice Guidelines for the Perioperative Management of Patients with Obstructive Sleep Apnea, the ASA and its consultants make the statement that “the potential for respiratory compromise should be considered in selecting intraoperative medications”. The ASA also makes the desirability of opioid reduction in this population clear by stating they “strongly agree that to reduce opioid requirements, nonsteroidal anti-inflammatory agents and other modalities (e.g., ice, transcutaneous electrical nerve stimulation) should be considered if appropriate”.

One medication that shows promise in the management of this group is ketamine. Ketamine is a dissociative anesthetic with well documented analgesic properties. The primary aspect of interest is that ketamine delivers pain relief which lasts beyond its expected effective time; it was found that preemptive administration of ketamine and administration of an infusion throughout abdominal surgery resulted in a decrease narcotic requirements when compared to the group who received a bolus of ketamine at abdominal closure; even though both groups had similar pain scores the infusion group had a lower narcotic requirement for two days after surgery.⁷ The next property of interest ketamine possesses is the fact that administration of ketamine has been shown to have a narcotic sparing effect.^{7,9,10} Another property of interest for the obese population is that ketamine maintains functional residual capacity (FRC) and increases the rib cage’s contribution to tidal breathing⁸ making respiratory depression less of a concern with ketamine than with narcotic pain medication immediately after the surgery, which can be important in a population (obese patients) already predisposed to sleep apnea.

A study performed by Fu compared pre-incisional ketamine along with an infusion to a single dose given post incision closure. After the surgery, pain scales and amount of narcotic used by each group were compared and an infusion of ketamine was found to decrease narcotic requirements more than a single bolus of ketamine.⁷ The proposed study compares a pre-incision bolus and intra-op infusion of ketamine to the standard practice of narcotic bolusing in gastric bypass surgery. Additionally this study will compare the total amount of narcotic used as well as average pain relief scores between the two groups. Therefore, the purpose of this research project is to determine if an intraoperative infusion of ketamine during bariatric surgery decreases narcotic requirements in the first 48 hours post operation.

Specific Aims: This study will attempt to determine if it is possible to reduce the post-operative opioid requirements for patients undergoing laparoscopic gastric bypass surgery while still providing acceptable levels of pain relief by utilizing an intra-operative infusion of ketamine. This study will compare two groups of patients presenting for gastric bypass surgery. The two groups will be randomized to a control group who will receive a standard, narcotic based pain relief anesthetic and the study group which will receive an intra operative ketamine infusion. After the surgery the patients’ narcotic use and pain scores will be followed for 48 hours to determine if the intra operative ketamine infusion is effective at decreasing post-operative narcotic requirements.

Research Plan: The study will be a head to head experiment with one group receiving narcotic medication during the surgery and the other group receiving a ketamine infusion. Both groups will receive 2 mg of versed on the way from pre op holding to the operating room, which is standard practice.

We plan to enroll at least 48 patients in this study, with 10 additional patients in case patients are removed from the study for any reason. This number was arrived at by a power analysis performed by [name] last year and it was estimated that to see a 30% reduction in narcotic use we would need two groups of 24, emphasizing that this would be a pilot study. The study by Fu utilized two groups of twenty participants each and found that “cumulative morphine consumption on D1 and D2 was reduced by approximately 40%”.⁷ The surgeon, [name], performs between three and five laparoscopic gastric bypasses per week so this number of patients should be able to be enrolled in a reasonable amount of time.

The ketamine group will receive 100 mcg of fentanyl at induction of anesthesia and then no further narcotics during the surgery. During induction the patient will receive a 20 mg bolus of ketamine, a dose of propofol deemed appropriate by the anesthesia team to render the patient unconscious and a dose of neuromuscular blocking medication followed by an intraoperative infusion of ketamine at 5 mcg/kg/min beginning after induction, and ending at the beginning of wound closure.

The narcotic group will receive no ketamine but rather a more standard anesthetic consisting of 100 mcg of fentanyl, a dose of propofol deemed appropriate by the anesthesia team to render the patient unconscious and a dose of neuromuscular blocking medication for induction. Intraoperatively only the narcotic group will be given intraoperative boluses of fentanyl and 0.3 mg of hydromorphone approximately 45 minutes prior to the end of surgery.

Both groups will receive 1 gram of Ofirmev (acetaminophen) infused over 15 minutes starting when wound closure begins. They will also both receive neuromuscular blockade reversal medication and a dose of Zofran at the end of the surgery. These medications are routine for this surgery. Anesthesia providers will be allowed to provide other non-analgesic medications to the patient which is consistent with their usual practice.

The amount of narcotics a patient receives is part of the medical record. Beginning in the PACU amount of narcotics needed to control the patient’s pain (converted to morphine equivalent units) and pain scores (a hospital standard measure) will be collected for 48 hours for the study, or until discharge, whichever occurs sooner. The conversion to a morphine equivalent unit is to allow us to compare different narcotics the patient may receive in a more standardized way. The results will be analyzed and compared between the two groups.

Patients will be eligible for inclusion in this study if they are between 18 and 65 years old presenting for laparoscopic gastric bypass surgery at Shands Hospital.

Patients would be excluded if they are below 18 or older than 65 or have hypersensitivity, allergy, or contraindications to fentanyl, propofol, hydromorphone or ketamine; the medications which could be administered in this study. Patients with cardiovascular disease who cannot tolerate the sympathomimetic effects of ketamine and ASA 4 patients will be excluded from this study.

Participants for this study will be recruited by [name] in his surgical clinic. If they are going to require gastric bypass surgery they will be informed of the study and asked to participate. The patients will be randomized into the two treatment groups utilizing a computer generated block randomization to get groups of equal size in each treatment. There will be 9 blocks of 6 and 1 block of 4 in order to evenly divide the 58 patients.

Patients PHI will be accessed by the study staff in collecting the data and clinicians in providing care to the patients. The only data which will be recorded will be pain scores and narcotic usage during the 48 hours after surgery. Consent for participation in the study will be scanned into the patient's record. Hard copies of the data will be saved in a locked drawer in [name] lock office until converted into a digital format, consistent with the department's protocol. The data will be analyzed with the help of the anesthesia departments statistical consultant.

Possible Discomforts and Risks: The patients will be undergoing gastric bypass surgery which, by its nature, is painful. They will be given FDA approved medications, consistent with their labeling, during the operation to minimize that pain. Post operatively the patients will be given whatever medications they need to control their pain. The largest potential side effects of ketamine is vivid dreams which may be unpleasant, this side effect should be blunted or avoided by the pre-operative administration of versed. As ketamine is a standard anesthetic drug, in the event of a temporary state of confusion or agitation related to ketamine the PACU would do as they do with any patient who has this reaction to ketamine and dim the lights and draw the curtains, allowing the patient to remain calmer as they wake from anesthesia. If the emergence is too distressing an additional dose of versed may be administered to blunt the reaction.

Possible Benefits: The patients could experience satisfactory pain relief while using less narcotics a goal recommended by the ASA. In receiving less narcotics the patients should have a lower incidence of negative side effects of narcotics including respiratory depression. The benefit to future patients will be if we are able to show that we can both decrease use of post-operative narcotics while maintaining satisfactory pain relief we can utilize this as a standard anesthetic regimen and avoid some of the negative and dangerous side effects of narcotics.

Conflict of Interest: Neither I nor the study team have any conflicts of interest involved in this study.

Bibliography:

1. Cdc.gov. Adult Obesity Facts | Data | Adult | Obesity | DNPAO | CDC. 2015. Available at: <http://www.cdc.gov/obesity/data/adult.html>. Accessed June 25, 2015.

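### Do the 10 spare patients, allowed for removals of any kind, let randomised patients be dropped in a way that biases the comparison?

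*Protocol*

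**What the plan says.** The sample-size paragraph of the Research Plan (Protocol) bases the target on an estimate that "to see a 30% reduction in narcotic use we would need two groups of 24". It plans for at least 48 patients, "with 10 additional patients in case patients are removed from the study for any reason". The randomisation paragraph uses 9 blocks of 6 and "1 block of 4 in order to evenly divide the 58 patients", so the spare patients are randomised like all the others.

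Three other statements in the Research Plan bear on the point:

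- After the induction dose of fentanyl, the ketamine group receives "then no further narcotics during the surgery", while the narcotic group is given fentanyl boluses and hydromorphone.
- On the outcome: "The amount of narcotics a patient receives is part of the medical record". Narcotic use and pain scores are collected from the PACU for 48 hours or until discharge, and the two groups are then compared.
- The paragraph on access to and storage of health information states: "The only data which will be recorded will be pain scores and narcotic usage during the 48 hours after surgery".

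**The concern.** Read together, these statements can look like an open door. Because all 58 patients are allocated, the removals that the margin covers include removals after allocation. No grounds are listed. The data sentence seems to leave the reason for a removal unrecorded.

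The arms also differ in a way that could link removal to treatment. An intraoperative narcotic after induction departs from the plan only in the ketamine arm, and a patient who needs one may well use more narcotic afterwards. If such patients were taken out, mean use in the ketamine arm would fall without any drug effect, and replacements would not correct it. At stake would be a false finding of narcotic sparing in a trial whose Possible Benefits section looks ahead to routine use of the regimen.

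**Working it through.** **1. The plan's own figures.** 48 + 10 = 58 and 9 × 6 + 4 = 58, which is 29 per arm. The margin is 10/58 = 17.2%. To keep 24 in each arm, at most 29 − 24 = 5 can be lost per arm. The figures agree with each other.

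**2. What 24 per arm implies.** The protocol gives no alpha, power or SD. Assuming two-sided 0.05, 80% power and the normal approximation, the detectable standardised difference is √(2/24) × (1.960 + 0.842) = 0.809. For a 30% reduction the implied CV is 0.30/0.809 = 0.37.

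**3. Size of the bias if removal were selective.** All inputs here are assumptions: no true effect, normal outcome, 29 per arm, two-sample t test at two-sided 0.05, 20,000 simulated trials per setting. Five patients are removed from each arm, at random in the control arm. In the ketamine arm they are removed in order of a score with the stated correlation to narcotic use. Every simulated trial keeps 24 per arm.

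| Correlation | False reduction, CV 0.37 | Two-sided error | False reduction, CV 0.70 | Two-sided error |
|---|---|---|---|---|
| 0 | about 0% | 4.7% | 0.2% | 5.4% |
| 0.3 | 3.4% | 6.2% | 6.5% | 6.4% |
| 0.5 | 5.5% | 8.3% | 10.3% | 8.7% |
| 1.0 | 11.0% | 21.7% | 20.9% | 21.7% |

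With 2 removed per arm and correlation 0.3, the false reduction is 1.5% (CV 0.37) or 2.8% (CV 0.70), with error 5.3% or 5.6%. A lognormal model with 3 or 5 removed from the ketamine arm only gives 2% to 7% at correlation 0.3 and 4% to 11% at 0.5. The same selective removal in both arms leaves the difference within 0.2% of zero.

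So the mechanism is real, but it needs selective removal that differs between the arms.

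**4. Does the text bring that condition about?**

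- *The margin sentence.* It explains an enrolment number. It gives nobody authority to drop a patient, names no deviation as grounds for removal, and ties removal to neither arm. Patients are recruited in a surgical clinic ahead of the operation, so cancelled surgery and withdrawn consent are ordinary reasons for a margin.
- *Follow-up.* Specific Aims and the Research Plan follow the randomised patients for 48 hours, or until discharge, and compare the groups. No exception is made for a patient who received a drug outside the plan.
- *The data sentence.* It stands in a privacy paragraph and describes what is taken from the chart. Read literally, it would also forbid recording the assigned arm, and then no comparison could be made. It therefore cannot show that removals go undocumented.
- *Checking removals by arm.* Once the list is filled, each arm has 29 allocated patients. 29 minus the number analysed gives the removals in that arm.

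**The case for a change.** The strongest contrary case is that this goes beyond a missing intention-to-treat clause. A SAP can define an analysis set, but it cannot recover reasons that were never recorded or outcomes that were no longer collected. The wording is wide enough to cover removal of a ketamine patient given an intraoperative narcotic, and the protocol describes no blinding of the treating team. Almost all of the extra error favours ketamine: with 5 removed per arm and correlation 0.3, significance in that direction occurs in 5.0% to 5.2% of simulated trials, against 2.5% nominal. If exactly the highest users were removed from the ketamine arm only, the lognormal model puts it as high as 31%.

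Part of this stands. The arithmetic is right, a full 24 per arm would not repair selective removal, and the protocol does not list the reason for a removal as a data item. What fails is the step from wide wording to a fault. The protocol does not say that removed patients are left out of the analysis, that deviations lead to removal, or that collection stops after a deviation. The outcome is in the medical record for anyone who has the operation. The 31% figure needs exact removal of the highest users from one arm, which nothing in the text suggests.

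**Conclusion.** The concern does not hold. The sentence is a routine allowance for attrition, its figures reconcile (48 + 10 = 58, 29 per arm), and following the protocol as written produces no arm-linked exclusion. The bias figures are conditional: about 3% to 7% at correlation 0.3 with 5 removed per arm, and larger only under stronger selection. They rest on assumed CVs, correlations and numbers removed, and on selection in one arm only. With removal unrelated to outcome, or equally selective in both arms, the false reduction is essentially nil.

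What would remain is a wish for an explicit analysis-set definition and a log of withdrawals. Protocols commonly leave both to the SAP, so their absence here is no error. This conclusion assumes that the analysis compares patients as randomised, which is the natural reading of the protocol. A SAP that excluded patients for intraoperative deviations would have to be judged separately.

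### The outcome is defined over 48 hours, but collection stops at discharge if that is sooner and discharge time is not among the data to be recorded, so totals and averages may cover unequal windows

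*Protocol*

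**What the plan says.** The Background gives the purpose as finding out whether the infusion "decreases narcotic requirements in the first 48 hours post operation", and names the summaries: "this study will compare the total amount of narcotic used as well as average pain relief scores between the two groups". The Specific Aims say that "narcotic use and pain scores will be followed for 48 hours". Neither place mentions discharge.

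The Research Plan gives the operational rule. Starting in the PACU, narcotic amounts and pain scores "will be collected for 48 hours for the study, or until discharge, whichever occurs sooner". On the data source it says: "The amount of narcotics a patient receives is part of the medical record". Its paragraph on privacy and data storage adds: "Patients PHI will be accessed by the study staff in collecting the data". The same paragraph then limits what is kept: "The only data which will be recorded will be pain scores and narcotic usage during the 48 hours after surgery". Discharge time is not mentioned there.

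**The concern.** A cumulative total depends on how long it is allowed to accumulate, and an average pain score depends on which hours are averaged. Under the collection rule both windows end at discharge for anyone who leaves before 48 hours. Discharge comes after randomisation and may be affected by treatment: the protocol itself expects less opioid and fewer opioid side effects with ketamine, and either could change readiness to leave.

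If early discharge differs by arm, part of any difference in totals reflects length of stay. The two outcomes are also distorted in opposite directions. Leaving early lowers the narcotic total. It raises the average pain score if pain falls over time, because only the earlier, more painful hours are averaged. The aim is less opioid with acceptable pain relief, so both halves of the conclusion are exposed. Without discharge times, a reader of the results could not tell whether this had happened.

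**Working it through.** **The passages side by side.** Background and Specific Aims: 48 hours, no exception. Research Plan, collection rule: the shorter of 48 hours and time to discharge. Research Plan, data list: pain scores and narcotic use only. The protocol gives no minimum stay, no collection after discharge and no rate per hour observed.

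**Inputs for an illustration.** From the protocol: "to see a 30% reduction in narcotic use we would need two groups of 24". It states no SD, alpha, power, length of stay or pattern of use over time, so everything else is assumed.

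- *Coefficient of variation (CV).* With a t test at two-sided 0.05, 24 per arm gives 80% power for a 30% reduction when the CV is 0.363. (The normal approximation gives 0.371.) The sample size cannot be reproduced without an SD; this only inverts it.
- *Share s of the 48-hour total accrued by time t.* Flat use: s = t/48. Use halving every h hours: s = (1 − 2^(−t/h)) / (1 − 2^(−48/h)).
- *Fraction p leaving early.* Varied by arm, and independent of a patient's narcotic use.

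**Formulas, no true effect.** Let S = s for early leavers and 1 otherwise, with the full 48-hour mean set to 1.

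- Arm mean = 1 − p(1 − s)
- Arm variance = E[S²](1 + 0.363²) − E[S]²
- Spurious reduction = 1 − (ketamine mean / control mean)
- False-positive rate from the noncentral t distribution, 24 per arm

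*Worked case:* discharge at 24 h, flat use, 50% ketamine against 25% control. s = 24/48 = 0.500. Ketamine mean = 1 − 0.50 × 0.50 = 0.750. Control mean = 1 − 0.25 × 0.50 = 0.875. Spurious reduction = 1 − 0.750/0.875 = 14.3%. The false-positive rate is 19.5%.

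**Narcotic totals** (spurious change, false-positive rate in brackets):

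| Early leavers, ketamine vs control | Discharge at | Flat use | Halving every 24 h | Halving every 12 h |
|---|---|---|---|---|
| Share s | 36 h | 0.750 | 0.862 | 0.933 |
| Share s | 24 h | 0.500 | 0.667 | 0.800 |
| 50% vs 25% | 36 h | −6.7% (9.3%) | −3.6% (6.3%) | −1.7% (5.3%) |
| 50% vs 25% | 24 h | −14.3% (19.5%) | −9.1% (12.4%) | −5.3% (7.7%) |
| 35% vs 25% | 36 h | −2.7% (5.7%) | −1.4% (5.2%) | −0.7% (5.1%) |
| 35% vs 25% | 24 h | −5.7% (7.2%) | −3.6% (6.1%) | −2.1% (5.4%) |
| 25% vs 50% | 36 h | +7.1% | +3.7% | +1.7% |
| 25% vs 50% | 24 h | +16.7% | +10.0% | +5.6% |

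Simulation of 40,000 trials per setting agreed for 50% vs 25%: 9.5%, 6.2% and 5.1% at 36 h; 19.8%, 12.3% and 7.8% at 24 h. With equal fractions and discharge times in both arms the ratio of mean totals is unchanged, although each total falls short of the 48-hour total.

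A real effect is distorted too. For 24 h and flat use, a true 30% reduction shows as 1 − 0.70 × 0.750/0.875 = 40.0% with 50% vs 25%, and as 1 − 0.70 × 0.875/0.750 = 18.3% with the fractions swapped.

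**Average pain.** If scores halve every h hours, the mean over 0 to T is proportional to (1 − 2^(−T/h)) / (ln 2 × T/h). The ratio r of the early leaver's mean to the 48-hour mean is 1.149 and 1.244 at 36 h, and 1.333 and 1.600 at 24 h (h = 24 and 12). With 50% vs 25%, ketamine pain is overstated by (1 + 0.5(r − 1)) / (1 + 0.25(r − 1)) − 1. That is 3.6% and 5.8% at 36 h, and 7.7% and 13.0% at 24 h. It is zero if scores are flat.

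**The case against.** The strongest reply is that an operational rule qualifying a summary is normal drafting: 48 hours can be read as an upper limit that the Research Plan makes explicit. The data list sits in a paragraph on privacy and storage and, taken literally, would also leave out treatment arm, so it is unlikely to be a complete list of variables. Discharge time is probably retrievable from the chart. How early leavers enter the analysis is commonly left to a SAP, which is not at hand.

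On size, every discharge figure above is assumed. The largest need a twofold gap between arms, discharge at 24 hours and flat use; with 35% vs 25% at 36 hours the error rate is essentially nominal. If the lightest users leave first, less is cut off: in the worst case (24 h, flat, 50% vs 25%) simulation with log-normal use gives about an 11% spurious reduction instead of 14%, and a false-positive rate of about 12% instead of 20%.

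Much of this stands as a limit on size, and none of it removes the point. Retrievable is not the same as planned, and nothing in the text says discharge time will be taken or reported. The conflicting window and the wording of the data list are in the protocol itself, whatever a SAP may add. The correlated-discharge case still leaves some inflation.

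**Conclusion.** The concern holds. The protocol states a 48-hour outcome and prescribes a window that ends at discharge. It compares summaries that depend on window length, and it does not list the variable needed to see whether the windows were equal.

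The textual defect is certain; its numerical effect is unknown and may be small. Bias between arms under no true effect requires discharge timing to differ by arm, and its direction cannot be predicted. Under the assumptions shown, a gap of 50% vs 25% in early discharge produces a spurious change that matters against a 30% target if patients leave at 24 hours (5–14%) and less if they leave at 36 hours (2–7%). The lower ends are more plausible if use declines over time. A gap of 35% vs 25% at 36 hours would be negligible. This should be fixed because the fix is cheap; confidence that it would change the result is moderate at most.

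**What to change.** - Reconcile the collection rule in the Research Plan with the 48-hour wording in the Background, the Specific Aims and the data paragraph. Describe the total collected to 48 hours or discharge as in-hospital use.
- Add discharge time, taken from the chart, to the recorded data. Report it by arm, with the number discharged before 48 hours.
- Alongside that total, compare charted narcotic use and pain scores over a common in-hospital window that essentially all patients complete, fixed before the data are compared. Zero to 24 hours from PACU arrival is one example; the protocol gives no length of stay to confirm it, so local discharge patterns should be checked first.
- Collecting home doses by phone to hour 48 is optional.

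**Cost.** One sentence, one chart field and one extra comparison. The common-window result answers a question about a shorter period than 48 hours. It keeps 80% power at 24 per arm only if the 30% reduction and a CV of 0.363 hold in that window; power is 72% at a CV of 0.40 and 62% at 0.45. The optional phone call would add recall error in early leavers only and may need a change to the consent.

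### The protocol restricts the recorded study data to pain scores and narcotic use, leaving out post-operative non-narcotic analgesics and the ketamine reactions it foresees

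*Protocol*

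**What the plan says.** The restriction stands in the paragraph of the Research Plan that deals with PHI, consent and data storage: "The only data which will be recorded will be pain scores and narcotic usage during the 48 hours after surgery". The other statements on data collection name the same two items. Under Specific Aims, the patients' "narcotic use and pain scores will be followed for 48 hours". In the Research Plan, narcotic amounts, converted to morphine equivalents, and "pain scores (a hospital standard measure) will be collected for 48 hours for the study, or until discharge, whichever occurs sooner", beginning in the PACU.

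On other drugs, the Research Plan is tighter during surgery than the protocol is afterwards. Both arms receive 1 gram of acetaminophen from the start of wound closure, and beyond the listed drugs "Anesthesia providers will be allowed to provide other non-analgesic medications to the patient". For the post-operative period, Possible Discomforts and Risks says that "the patients will be given whatever medications they need to control their pain". The Background cites professional guidance that, "to reduce opioid requirements, nonsteroidal anti-inflammatory agents and other modalities", should be considered where appropriate.

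On ketamine reactions, Possible Discomforts and Risks names vivid dreams as the main potential side effect, describes what the PACU does "in the event of a temporary state of confusion or agitation related to ketamine", and allows for a further dose of versed if emergence is too distressing.

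**The concern.** The outcome is narcotic consumption, with pain scores to show that relief is acceptable. Both can be influenced by non-narcotic analgesics given after surgery. The protocol controls analgesic additions in the operating room, but sets no such limit during the period when the outcome is measured, and it does not plan to record what is given. A reader of the results who asks what else patients received for pain, and whether it was similar in the two arms, would find no answer in the study data.

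The ketamine reactions raise a second question. Possible Benefits looks ahead to using the regimen as a standard anesthetic if narcotic use falls while pain relief is maintained. Anyone weighing that step would want to see how often the reactions named in the protocol occurred in each arm. They are not among the planned data, and neither is the extra versed given for them.

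**Working it through.** The protocol states no figure on this point to reproduce, so the check sets its statements side by side.

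**Step 1: what is planned as post-operative data.** Three places describe it:

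- Specific Aims: narcotic use and pain scores, for 48 hours.
- Research Plan, data-collection paragraph: narcotics in morphine equivalents and pain scores, from the PACU to 48 hours or discharge, whichever is sooner.
- Research Plan, PHI paragraph: these two items *only*.

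The three lists name the same two items. None adds a third.

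**Step 2: what the protocol itself expects or allows after surgery, and whether it is in that list.**

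| Item | Where mentioned | In the planned data? |
|---|---|---|
| Narcotic doses | Specific Aims; Research Plan | Yes |
| Pain scores | Specific Aims; Research Plan | Yes |
| Non-narcotic analgesics after surgery | Allowed, not scheduled, under Possible Discomforts and Risks; nonsteroidal agents cited in Background | No |
| Vivid dreams, confusion, agitation | Possible Discomforts and Risks | No |
| Additional versed for a reaction | Possible Discomforts and Risks | No |

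The morphine-equivalent conversion does not close the third row, because it puts different narcotics on one scale and covers nothing else. Versed is not a narcotic, so the last row is not captured as narcotic use.

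**Step 3: could a statistical analysis plan repair this?** An analysis plan decides how recorded data are used. It cannot analyse items that the protocol says will not be recorded. The point therefore concerns something this document fixes, not something left for later.

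**Step 4: extent.** Planned enrolment is 48 + 10 = 58, which agrees with the randomisation blocks: 9 × 6 + 4 = 58. The restriction applies to all 58 charts.

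**Step 5: can an effect on the result be sized?** No. A shift in the difference between arms would depend on how far the arms differ in the proportion given a co-analgesic, and on how much such a drug lowers a user's narcotic need. The protocol gives neither. The only effect size it states is the planning target, "to see a 30% reduction in narcotic use we would need two groups of 24", and nothing in the text allows a co-analgesic effect to be set against it.

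**The case against.** The strongest reply has four parts.

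First, the sentence sits among statements on PHI access and storage and may be meant as a privacy limit. Read with full literalness it would exclude even treatment arm and age, which the study plainly needs. This stands as a caution about the word *only*. It does not supply the missing items: even as a privacy limit, the sentence fixes what study staff may record, and the two other descriptions of post-operative data name nothing more.

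Second, the aims are narcotic use and acceptable pain relief, the protocol collects exactly those, and it calls the study a pilot. This also stands, so the point is an improvement and not a contradiction. A pilot does, however, gain from describing co-treatment and tolerability.

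Third, co-analgesic use arises after randomisation. If ketamine changes pain, it may change all analgesic use, and that is part of the treatment effect under usual care. Chance differences between the arms are already reflected in the standard error. This stands in full. A reader might infer that unrecorded co-analgesics bias the narcotic comparison, or that they should be adjusted for. The document supports neither: it shows no imbalance, it does not say that non-narcotic analgesics will in fact be given after surgery, and adjustment would condition on a post-randomisation variable.

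Fourth, the items may be in the medical record, so they may be retrievable later with an approved change. That is correct. The claim is limited to the planned study dataset and does not say that the information is lost. In addition, consent pages are not part of the text at hand, so any safety-reporting wording there cannot be judged.

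**Conclusion.** The point holds as a cheap improvement worth making. As written, the study dataset could describe neither non-narcotic analgesic use beside the narcotic and pain outcomes nor the foreseen ketamine reactions and extra versed by arm. This applies to all 58 planned patients. No numerical effect on the result can be derived from the document, and none is claimed. The randomised comparison of narcotic use remains valid.

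Two further readings are tempting and are not supported. A reader might take the passage on future standard use, under Possible Benefits, as an adoption rule resting solely on narcotic use and pain relief. It is a statement of hope and sets no such rule. A reader might also treat the expected fall in narcotic side effects, including respiratory depression, as an endpoint that the trial omitted to measure. It appears as rationale in the Abstract and under Possible Benefits, but not in the Specific Aims, so no declared endpoint is missing.

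The conclusion assumes that the PHI paragraph governs what enters the study dataset, and that no part of the protocol outside the text at hand lists further post-operative data.

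**What to change.** Replace the restrictive sentence in the Research Plan with a list of the post-operative data to be abstracted from the chart, over the window already set there (PACU to 48 hours or discharge, whichever is sooner):

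- pain scores;
- narcotic doses;
- non-narcotic analgesic doses;
- charted ketamine reactions, with any extra versed doses.

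State that the added items will be reported descriptively by arm, and that the narcotic comparison will not be adjusted for post-randomisation co-analgesic use. Add a note that reactions charted passively, dreams above all, may be under-counted, so that low counts are not read as evidence of absence.

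The cost is extra abstraction for 58 charts and matching changes to the PHI and consent wording. No extra patients or procedures are needed, and treatment does not change. Reactions that staff do not chart would still be missed.
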